### **7.1.4 Physical Examinations**

A full physical examination, including body temperature (oral preferred for participants  $> 4$  years of age, tympanic preferred for participants  $\leq 4$  years of age, but other methods are acceptable in context of COVID-19 precautions), length/height and weight, will be performed at the Screening Visit or on Day 1. For participants receiving booster doses, symptom-directed physical examination will be performed on BD-Day 1. The full examination will include assessment of

skin, head, ears, eyes, nose, throat, neck, lungs, heart, abdomen, lymph nodes, and musculoskeletal system/extremities. Any clinically significant finding identified during a study visit should be reported as an MAAE.

Symptom-directed physical examinations will be performed per the SoAs found in [Section 10.1](#) (Appendix 1) and may be performed at other time points at the discretion of the investigator. Body temperature (oral/tympanic) should be measured on each injection day prior to injection. On each injection day before injection and again 7 days after injection (ie, the day of injection and 6 subsequent days), the injection site should be examined. Any clinically significant finding identified during a study visit should be reported as an MAAE.

Participants who are febrile (body temperature  $\geq 38.0^{\circ}\text{C}/\geq 100.4^{\circ}\text{F}$ ) before injection on Day 1 or Day 29 must have the visit rescheduled within the relevant visit window to receive the injection. Afebrile participants with minor illnesses may be injected at the discretion of the investigator.

Body mass index will be calculated for children  $\geq 2$  years of age at the Screening Visit only.

### 7.1.5 Assessment for SARS-CoV-2 Infection

Study participants will have nasal swab samples collected for SARS-CoV-2 testing at the time points specified in in the SoAs ([Section 10.1](#)).

While Part 2 of the study is still blinded for any age group, a study illness visit (study site visit or home visit) will be arranged within 72 hours or as soon as possible if a participant experiences any of the following:

- Signs or symptoms of SARS-CoV-2 infection as defined by the CDC ([CDC 2020b](#))
- MAAE suggesting a SARS-CoV-2 infection

For asymptomatic children, a study visit (study site visit or home visit) will be arranged approximately 7 days after the diagnosis of COVID-19 in a household, if a participant experiences the following:

- Exposure (close contact [definition in [Section 7.1.1](#)]) to an individual in the household confirmed to be infected with SARS-CoV-2. For the purpose of calculating the day of the study visit, 7 days will be calculated from the first day of illness or positive COVID-19 test, whichever day is earlier, in a household contact.

A negative local diagnostic test (NAAT) may be used to satisfy the study visit, provided that the participant remains asymptomatic for COVID-19 and the test is collected at least 5 days after the index case in a household.

In accordance with CDC guidance on COVID-19 testing, exposure visits are not required for participants who are within 90 days of a COVID-19 illness (from the date of positive COVID-19

test). Illness visits should still be performed, even if within 90 days of a previous COVID-19 infection, for participants with signs/symptoms consistent with COVID-19.

During a surge in SARS-CoV-2 infections across the US and Canada and given the changing practice of using home tests to diagnose SARS-CoV-2 infections, the following alternative process may be used for assessment of SARS-CoV-2 infection:

If an illness visit is not feasible due to COVID-19 related restrictions at site or in the wider community, a telehealth visit or phone call combined with a local diagnostic test to be recorded under an unscheduled visit eCRF page, can substitute for a clinic visit.

If due to COVID-19 related restrictions in the community, the participant's LAR performed a home test rather than obtaining a test performed by a health care professional, the following process should apply:

- If the participant is asymptomatic but was exposed to a positive household member, and the home test obtained within the appropriate window (4-6 days post-exposure) was **negative**, the investigator may report the result of the home test under the local diagnostic lab page as an unscheduled visit and forego the illness visit.
- If the participant reports symptoms but home test was **negative**, the investigator may report symptoms as 'URI' or other appropriate AE and report the negative home test on the local diagnostic lab page for an unscheduled visit, and forego the illness visit.
- If the participant reports symptoms, or is asymptomatic after a household exposure, and the home test was **positive**, the investigator should encourage the family to seek confirmatory PCR-based testing at a local testing center or return to site for an illness visit.
  - If a local confirmatory PCR-based test is obtained, the investigator may report the result under an unscheduled visit and forego the illness visit.
  - If due to COVID-19 related restrictions at the site or in the community, neither a local test nor an illness visit is feasible, the investigator may report the result of the home test under the local diagnostic lab page as an unscheduled visit and forego the illness visit.

If the participant had a known exposure (close contact) to COVID-19 (eg, exposure to someone with confirmed COVID-19 in the household), it will be captured in the COVID-19 exposure form.

Additionally, clinical information will be carefully collected to evaluate the severity of the clinical case.

At each study illness visit, an initial assessment will be performed to determine general appearance. This initial assessment may be performed by physicians, advanced practice nurses, physician assistants, or registered nurses. If indicated, a physical examination by a study clinician (MD, DO, NP, or PA experienced in pediatric examination) may occur.

The study illness visit (study site visit or home visit) may collect additional clinical information, including assessments such as updated medical history, physical examination, blood sampling for clinical laboratory testing, and nasal swab sampling for viral RT-PCR to evaluate the severity of the clinical case. Radiologic imaging studies may be conducted. Study site may also collect an additional nasal swab sample for SARS-CoV-2 testing to be able to render appropriate medical care for the study participant as determined by local standards of care. All findings will be recorded in the eCRF.

If participants are confirmed to have SARS-CoV-2 infection, the investigator will notify the participant's parent(s)/LAR(s) and the participant's primary care physician of the diagnosis via fax or other Health Information Portability and Accountability Act compliant electronic data transfer (eg, e-mail if applicable). If the study participant does not have a primary care physician, the investigator will assist them to obtain one. The participant will also be instructed on infection prevention measures consistent with local public health guidance. Laboratory test results for SARS-CoV-2 infection in study participants should be submitted to state or local public health departments according to local policy. The investigator must either directly report to state or local public health department or obtain confirmation from the participant's primary care physician that the positive test was reported.

Any confirmed symptomatic SARS-CoV-2 infection that occurs in participants will be captured as an MAAE along with relevant concomitant medications and details about severity, seriousness, and outcome. Additionally, a convalescent visit may be scheduled approximately 28 days (+7 days) after diagnosis ([Section 7.3.3](#)) if there are any doubts about the initial diagnosis (at the discretion of the principal investigator [PI]). At this visit a blood sample for potential immunologic assessment of SARS-CoV-2 infection will be collected.

If a participant tests positive at baseline but remains asymptomatic and there are doubts about the validity of the positive test, Day 29 visit can be used as the convalescent visit to obtain a convalescent blood sample (at the discretion of the PI); the second dose may still be administered as long as participant remains asymptomatic and no other concerns arise.

Once the trial is unblinded for all age groups and thus no placebo comparator group is available going forward, illness visits for COVID-19 symptoms or exposures and convalescent visits will no longer be required. COVID-19 will then be reported under regular AE reporting as per SoA.

## 7.2 Blood Collections for Immunogenicity Assessments and Biomarker Samples

Blood samples for immunogenicity assessments and biomarker samples will be collected at the time points indicated in the SoAs ([Section 10.1](#)). The following analytes will be measured:

- Serum nAb titer against SARS-CoV-2 as measured by pseudovirus and/or live virus neutralization assays.
- Serum bAb titer as measured by enzyme-linked immunosorbent assay specific to the SARS-CoV-2 S protein.
- For Part 1, testing for serologic markers for SARS-CoV-2 infection using a nonvaccine antigen-based blood test at Day 1 (prior to the first dose), Day 57, Day 209, and Day 394.

For Part 2, participants in each age group will be assigned to 5 phlebotomy cohorts. Blood sampling will be performed in 3 of these 5 cohorts for immunogenicity at 3 of the following time points: Day 1 (prior to randomization and the first dose), Day 57, and one of Day 29 (prior to the second dose), Day 209, and Day 394. Participants in the Cohort D (remainder of the age group) will provide a blood sample at Day 1 (prior to randomization and the first dose) and within 4 days of receiving Dose 2 at Day 30 (+3 days) for storage and potential future biomarker testing (may include cardiac biomarkers). For participants already enrolled in Cohort D prior to Amendment 4, this blood draw will be optional and confirmed at time of re-consenting; for all participants newly enrolled into Cohort D under Amendment 4, it will be mandatory. A fifth cohort of participants at selected VTEU sites only, will provide blood samples for assessment of exploratory serology and CMI on Day 1 (prior to randomization and the first dose), Day 43, Day 209, and Day 394.

All participants in Part 3 of the study will provide blood specimens for immunogenicity on Day 1 (prior to the first dose) and will also provide additional samples at Day 57, Day 149/BD-Day 1, one month after the third dose on Day 177/ BD-Day 29. The first 150 participants (Sub-Cohort F) will also have a blood draw on Day 329/BD-Day 181; the second 150 participants (Sub-Cohort G) will also have a blood draw on Day 514/BD-Day 366.

All participants in Part 1 and Part 2 who choose to receive a booster dose will provide a blood specimen for immunogenicity and serostatus on BD-Day 1; a subgroup of participants will also provide one additional blood specimen for immunogenicity. Please see [Table 16](#) for details.

Sample aliquots will be designed to have backup samples, if possible; vial volumes will likely be adequate for future testing needs. The actual time and date of each sample collected will be recorded in the eCRF, and unique sample identification will be utilized to maintain the blind at the laboratory at all times and to allow for automated sample tracking and housing. Handling and

preparation of the samples for analysis, as well as shipping and storage requirements, will be provided in a separate study laboratory manual.

Measurement of bAb and nAb levels will be performed in a laboratory designated by the Sponsor.

According to the ICF section ([Section 10.2.6](#)), serum from immunogenicity testing may be used for future research, which may be performed at the discretion of the Sponsor to further characterize the immune response to SARS-CoV-2, additional assay development, and the immune response across CoVs.

The planned volume of blood to be sampled per participant in Part 1, Part 2, and Part 3 (serology cohorts) for each age group for immunogenicity assessments in 1 day is as follows:

- 6 months to < 2 years: approximately 8 mL
- 2 years to < 6 years: approximately 16 mL
- 6 years to < 12 years: approximately 24 mL

The planned volume of blood to be sampled per participant at the Day 30 (+3 days) blood draw for storage and potential future biomarker testing for Cohort D in Part 2 is as follows:

- All ages: approximately 4 mL

The planned volume of blood to be sampled per participant in the exploratory serology and CMI cohort for each age group in 1 day is as follows:

- 6 months to < 2 years: approximately 9 mL
- 2 years to < 6 years: approximately 9 mL
- 6 years to < 12 years: approximately 17 mL

Note: If less than 8 mL of blood is obtained for any given child at baseline, except for Cohort D for 6 months to < 2 years, where 4 mL can be obtained, the child cannot be enrolled.

Blood volumes for Booster phase:

- BD-Day 1 (pre-booster) and post-booster draw for 2 year to < 12-year-old children (at time of booster): approximately 8 mL.
- BD-Day 1 (pre-booster) and post-booster draw for 6 months to < 2 year-old children (at time of booster): approximately 4 mL.

## 7.3 Inferred Efficacy Assessments

### 7.3.1 Vaccine Effectiveness Assessments

Vaccine effectiveness for children 6 months to < 12 years of age will be inferred based on serum antibody responses obtained on Day 57 (28 days after the second injection of mRNA-1273). Inference will be based on assessing the antibody responses against the following:

1. *If available at the time of analysis*, antibody responses will be assessed against an accepted serum antibody threshold conferring protection against COVID-19.
2. *If an accepted threshold of protection is not available*, noninferiority of the GM value of serum antibody and SRR of children 6 months to < 12 years of age (Study P204) compared with the GM value of serum antibody and SRR from young adults (18 to 25 years of age) enrolled in the ongoing clinical endpoint efficacy trial (Study P301) will be assessed. The statistical parameters to infer effectiveness are described in [Section 8](#).

### COVID-19:

To be considered as a case of COVID-19 for the evaluation of the efficacy endpoint, the following case definition must be met:

- The participant must have at least 1 nasal swab (or respiratory sample, if hospitalized) positive for SARS-CoV-2 by RT-PCR AND
- ONE of the following:
  - Fever (temperature  $\geq 38^{\circ}\text{C}/\geq 100.4^{\circ}\text{F}$ ) or chills (of any duration, including  $\leq 4$  hours)
  - Shortness of breath or difficulty breathing (of any duration, including  $\leq 48$  hours)
  - Cough (of any duration, including  $\leq 48$  hours)
  - Fatigue
  - Muscle or body aches
  - Headache
  - New loss of taste or smell
  - Sore throat
  - Congestion or runny nose
  - Abdominal pain
  - Nausea or vomiting
  - Diarrhea

- Poor appetite/poor feeding

**Severe COVID-19:**

To be considered severe COVID-19, the following criteria must be met:

- Confirmed COVID-19 as per the COVID-19 case definition, plus any of the following:
  - Meeting criteria for systemic inflammatory response syndrome based on age -specific variables ([Table 6](#)) OR
  - Respiratory failure or acute respiratory distress syndrome (defined as needing high-flow oxygen, noninvasive or mechanical ventilation, or extracorporeal membrane oxygenation), medical intervention for shock (intravenous fluids, vasopressors, etc), OR
  - Significant acute renal, hepatic, or neurologic dysfunction ([Table 7](#)), OR
  - Admission to an ICU or death.

**Table 6: Age-Specific Cut-Offs for Vital Signs and Laboratory Variables**

Age Group	Heart Rate, Beats/Min		Respiratory Rate, Breaths/Min	Leukocyte Count, Leukocytes $\times 10^3/\text{mm}^3$	Systolic Blood Pressure, mm Hg
	Tachycardia	Bradycardia			
1 month to 1 year	> 180	< 90	> 34	> 17.5 or < 5	< 70
2 years to 5 years	> 140	NA	> 22	> 15.5 or < 6	< 70 + (age in years x 2)
6 years to 10 years	> 130	NA	> 18	> 13.5 or < 4.5	< 70 + (age in years x 2)
>10 years	> 130	NA	>18	> 13.5 or < 4.5	< 90

Abbreviations: AHA = American Heart Association; NA = not applicable.

Note: Lower values for heart rate, leukocyte count, are for the 5th percentile and upper values for heart rate, respiratory rate, or leukocyte count are for the 95th percentile for that age group. Systolic blood pressure values are based on AHA definitions of hypotensive shock for pediatric population.

Source: [Goldstein et al 2005](#) and [Topjian et al 2020](#).

**Table 7: Definition of Renal-, Liver- and Neurological Dysfunction for Pediatric Population (< 12 years of age)**

Acute Renal Dysfunction	
 
• Increase in serum creatinine by <math>\geq 0.3</math> mg/dL (<math>\geq 26.5</math> <math>\mu</math>mol/L) within 48 hours; OR
 
• Increase in serum creatinine to <math>\geq 1.5</math> times baseline, known or presumed to have occurred within prior 7 days OR
 
• Urine volume <math>\leq 0.5</math> mL/ kg/ hour for 6 hours
 

Acute Liver Dysfunction	
 
• <math>> 3</math>-fold elevation above the upper normal limit for ALT or AST OR
 
• <math>> 2</math>-fold elevation above the upper normal limit for total serum bilirubin or GGT or ALP
 

Acute Neurological Dysfunctiona	
ANY of the following:
 
 
• Loss of sense of smell or taste
 
• Seizures or status epilepticus
 
• Severe headache (preventing normal daily activities)
 
• Persistent difficulty walking or crawling (if crawling/walking before)
 
• Persistent altered awareness or confusion (preventing normal daily activities)
 
• Persistent severe fatigue or weakness (preventing normal daily activities)
 

Abbreviations: ALT = alanine aminotransferase; ALP = alkaline phosphatase; AST = aspartate aminotransferase; GGT = gamma-glutamyl transferase.

Source: a[LaRovere et al 2021](#).

Death attributed to COVID-19 is defined as any participant who dies during the study with a cause directly attributed to a complication of COVID-19.

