#### 7.4.4 Medically Attended Adverse Events

An MAAE is an AE that leads to an unscheduled visit to an HCP. This would include visits to a study site for unscheduled assessments (eg, abnormal laboratory test result follow-up, COVID-19 [[Section 7.3.1](#)]) and visits to HCPs external to the study site (eg, urgent care, primary care physician). Investigators will review unsolicited AEs for the occurrence of any MAAE. Unsolicited AEs will be captured on the AE page of the eCRF.

While COVID-19 surveillance is ongoing, all confirmed symptomatic COVID-19 cases ([Section 7.3.1](#)) will be recorded as MAAEs. Any severe COVID-19 cases will be reported to the Sponsor or designee immediately and in all circumstances within 24 hours, using the SAE Mailbox, the SAE Hotline, or the SAE Fax line ([Section 7.4.11](#)). The investigator will submit any updated COVID-19 case data to the Sponsor within 24 hours of it being available.

Once COVID-19 surveillance is discontinued, COVID-19 related AEs will be reported per standard AE reporting for the respective SoA.

All suspected cases of anaphylaxis should be recorded as MAAEs and reported as an SAE, based on criteria for a medically important event, unless the event meets other serious criteria. As an SAE, the event should be reported to the Sponsor or designee immediately and in all circumstances within 24 hours as per [Section 7.4.11](#). The investigator will submit any updated anaphylaxis case data to the Sponsor within 24 hours of it being available. For reporting purposes, a participant who displays signs/symptoms consistent with anaphylaxis as described below should be reported as a potential case of anaphylaxis. This is provided as general guidance for investigators and is based on the Brighton Collaboration case definition ([Rüggeberg et al 2007](#)).

Anaphylaxis is an acute hypersensitivity reaction with multi-organ-system involvement that can present as, or rapidly progress to, a severe life-threatening reaction. It may occur following exposure to allergens from a variety of sources.

Anaphylaxis is a clinical syndrome characterized by:

Sudden onset AND

Rapid progression of signs and symptoms AND

Involves 2 or more organ systems, as follows:

- **Skin/mucosal:** urticaria (hives), generalized erythema, angioedema, generalized pruritus with skin rash, generalized prickle sensation, red and itchy eyes

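### Loss of smell or taste alone, with a positive RT-PCR, meets both the ordinary and the severe COVID-19 definition, so the severe count needs a companion count without these cases

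*Protocol*

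**What the plan says.** Section 7.3.1 defines COVID-19 by a virological condition, "The participant must have at least 1 nasal swab (or respiratory sample, if hospitalized) positive for SARS-CoV-2 by RT-PCR AND" at least one symptom from a list. That list includes "New loss of taste or smell", as well as headache and fatigue.

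Severe COVID-19, in the same section, is "Confirmed COVID-19 as per the COVID-19 case definition, plus any of the following". One of the alternatives is "Significant acute renal, hepatic, or neurologic dysfunction", with a pointer to Table 7. The others are systemic inflammatory response criteria, respiratory failure or shock, and ICU admission or death.

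Table 7 is titled as the definition of renal, liver and neurological dysfunction. Its neurological row requires "ANY of the following" and opens with "Loss of sense of smell or taste". The remaining items are seizures or status epilepticus, severe headache that stops normal activity, and persistent problems with walking or crawling, awareness, or fatigue and weakness.

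Sections 7.3.2 and 7.3.3 leave it to the investigator to decide whether the severe criteria are met. Section 7.4.4 attaches a reporting duty to the label while surveillance runs: "Any severe COVID-19 cases will be reported to the Sponsor or designee immediately and in all circumstances within 24 hours", by the SAE mailbox, hotline or fax.

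**The concern.** A severity class should need something beyond what makes a case in the first place. Here one symptom does both jobs. An otherwise well child with isolated loss of taste and a positive swab falls into the same class as a child with respiratory failure or an ICU admission.

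Headache and fatigue are also case-defining symptoms, and Table 7 raises the bar for both before they count as neurological dysfunction. For smell and taste it sets no bar and even omits the word that limits the case-definition symptom to new onset. The contrast suggests an oversight rather than an intended threshold.

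Three things are at stake: the exploratory description of clinical severity (Section 2, Table 2), any table of severe cases by arm, and the route by which severe cases are reported. No adjudication of severe COVID-19 is described, so sites may also apply the item differently.

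**Working it through.** **No planned figure to reproduce.** The protocol states no rate, sample size or power for severe COVID-19. The check is a trace through the definitions, followed by an illustration of size.

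**Trace (Section 7.3.1 and Table 7).**
1. RT-PCR positive and new loss of taste or smell: a confirmed COVID-19 case.
2. Loss of smell or taste is one of the Table 7 neurological items, and one item is enough: acute neurological dysfunction.
3. Confirmed case plus neurological dysfunction: severe COVID-19.

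No further sign is needed at any step.

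**Size.** Let a be the share of confirmed cases with loss of smell or taste, and s the share that are severe on any other criterion. If the two are independent:

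- severe share as written = 1 − (1 − a)(1 − s)
- proportion of severe cases that qualify only by smell or taste = [severe share − s] / severe share

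The protocol does not give a, so it is assumed, from 0.5% to 10%. For s, Section 1.1 reports that 1.2% of school-aged children with COVID-19 were hospitalized. That figure serves as a proxy, and 3% is an assumed alternative.

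Worked case, s = 1.2% and a = 1%: severe share = 1 − 0.99 × 0.988 = 2.19%. Proportion by this item alone = (2.19 − 1.2)/2.19 = 45%.

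Worked case, s = 1.2% and a = 5%: severe share = 1 − 0.95 × 0.988 = 6.14%. Proportion = (6.14 − 1.2)/6.14 = 80%.

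| a (assumed) | Severe share, s = 1.2% | By this item alone | Severe share, s = 3% | By this item alone |
|---|---|---|---|---|
| 0.5% | 1.69% | 29% | 3.49% | 14% |
| 1% | 2.19% | 45% | 3.97% | 24% |
| 2% | 3.18% | 62% | 4.94% | 39% |
| 5% | 6.14% | 80% | 7.85% | 62% |
| 10% | 11.08% | 89% | 12.70% | 76% |

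The proportion passes one half when a exceeds s/(1 − s). That is 0.012/0.988 = 1.2% of cases for the hospitalization proxy, and 0.03/0.97 = 3.1% for s = 3%.

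**The case against.** The strongest reply concerns consequences.

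**Reach.** Severe COVID-19 is not a primary or secondary endpoint (Section 2, Table 2), and Section 8.5.4 plans no comparison of it by arm. The COVID-19 pause rules in Table 5 name death and ICU admission directly. This stands. A reader might infer from Section 1.2.2 that severe COVID-19 by arm is the trial's measure of vaccine-enhanced disease, so that a real imbalance would be hidden or a false one created. The section does not say so. It discusses that risk through animal studies, Phase 1 immunogenicity and adult Phase 3 data, and names no measure for this study.

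**Reporting.** Appendix 4 already makes new anosmia or ageusia associated with COVID-19 an AESI, unless it is due to nasal congestion. Section 7.4.5 requires AESIs to be reported within 24 hours. This also stands: for most such children the severe label changes the route more than the clock.

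**Size.** The symptom rate is assumed, and hospitalization may understate severity on the other criteria, several of which need no admission. With s = 10% (assumed) and a = 5%, the proportion falls to (14.5 − 10)/14.5 = 31%. So the documents do not support the inference that the severe count mainly measures smell or taste loss, or has lost its meaning.

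**Discretion.** The neurological row cites a source, and Section 7.3.1 speaks of significant dysfunction, judged by the investigator. This is weak: Table 7 is the stated definition and gives no threshold for this item.

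**Age groups.** Very young children can hardly report the symptom, but the same is true of headache or sore throat in the ordinary definition. This alone does not set the item apart.

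**Conclusion.** The overlap is certain on the text and needs no outside fact: one case-defining symptom is by itself sufficient for severe COVID-19. It bears on the exploratory severity description, any severe-case table and SAE-route reporting, and on nothing confirmatory.

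Its numerical weight is unknown. Under independence, with 1.2% severe on other criteria, the item alone would account for about 45% of severe cases at a symptom rate of 1% and about 80% at 5%. With 3% severe on other criteria, the range is 14% to 76% for symptom rates of 0.5% to 10%. If children with smell or taste loss also tend to meet another criterion, the proportions are lower.

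A reader might conclude that the item should simply be struck from Table 7 and severe status re-derived. The documents do not support that now. The Amendment 9 summary of changes states that all age groups are unblinded, so deletion would alter a prespecified case definition after the fact. A supplementary count gives the same information without doing so. This is a cheap improvement to interpretability.

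**What to change.** Reconcile the COVID-19 definition, the severe COVID-19 definition and Table 7 by stating whether loss of smell or taste alone meets the severe criterion.

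Keep the prespecified severe count as it is. Beside it, report by arm and age group the severe count excluding cases that qualify only by this item, and list those cases separately.

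The cost is one supplementary table and a listing, derived from symptoms already recorded, with no new data collection. The addition must be labelled as made after unblinding, which limits it to a descriptive role.
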